### **9.1.8 Event-free survival (EFS)**

Time from treatment start until date of first documented event. Event will be defined as: confirmed relapse, withdrawal from study due to adverse event, or death due to any cause.

### **9.1.9 CR duration (CRd)**

Time from CR or Cri until date of first objective documentation of confirmed relapse.

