### 1.2 Secondary objective

- To assess overall survival (OS) of patients with AML treated with lenalidomide maintenance.
- To assess event-free survival (EFS) of patients with AML treated with lenalidomide maintenance.
- To assess the duration of remission (CRd) of patients with AML treated with lenalidomide maintenance.
- To assess toxicity and safety of lenalidomide maintenance in patients with AML.
- To assess the effects of lenalidomide maintenance on NK cell modulation and dynamics of minimal residual disease and their relationship to outcomes.

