## 3.0 PATIENT SELECTION

### 3.1 Inclusion Criteria:

1. Patients aged 18 to 55 years with high risk (as defined in #2) AML who have achieved their **FIRST** CR or CRi within 12 months of enrollment and are not immediately candidates for allogeneic stem cell transplant. Patients above age 55 who are not eligible for other protocols may be considered for enrollment on a case by case basis after discussion with the PI.
2. Patients in their **FIRST** CR or CRi may be eligible for enrollment only if they have a high risk feature, including, but not limited to: adverse karyotype, FLT3 mutation, history of antecedent hematologic disorder (AHD), presence of dysplasia in the bone marrow, therapy-related AML, history of requiring more than 1 cycle of intensive induction chemotherapy to achieve first remission, or presence of persistent minimal residual disease (detected by cytogenetics, molecular markers, or flow cytometry) at any point after initial induction cycle. Patients aged > or = 18 years with AML who have achieved a **SECOND** CR or CRi within 12 months of enrollment and are not immediately candidates for allogeneic stem cell transplant are also eligible.
3. Patients should have received induction chemotherapy for AML and at least 1 consolidation.
4. Patients with history of extramedullary AML, except for CNS involvement that is currently controlled, will not be eligible for enrollment.
5. ECOG performance status of < or = 3
6. Adequate organ function as follows:
  - a. Serum total bilirubin < or = to 1.5 X the Upper Limit of Normal (ULN)
  - b. Serum creatinine < or = to 2.5 x ULN
7. Adequate BM reserve:
  - a. Absolute neutrophil count (ANC) > 0.5 x 10^9/L
  - b. Platelet count > or = 30 x 10^9/L

8. For females of childbearing age, they may participate if they:
  - a. Have a negative serum or urine pregnancy test within 10 to 14 days of enrolling  
(A second pregnancy test will be performed within 24hrs of starting therapy and both negative pregnancy tests will be required for starting therapy.)
  - b. Agree to either abstinence or 2 effective contraceptive methods throughout the treatment period and up to 28 days after discontinuing treatment.
9. For male patients with a female partner of childbearing age, they may participate if they agree to either abstinence or 2 effective contraceptive methods throughout the treatment period and up to 28 days after discontinuing treatment.

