## 8.0 STATISTICAL CONSIDERATIONS

### STATISTICAL CONSIDERATIONS

This is a phase II study of lenalidomide as a maintenance therapy in patients with high risk AML and in first or second remission. The primary objective is to assess whether the maintenance therapy can improve relapse-free survival (RFS), which is defined as the time interval from date of treatment start until the date of death or disease relapse. Patients who are alive and relapse-free at the last follow-up date will be censored at that time.

The study will be continuously monitored for the primary endpoint, RFS, using the method of Thall, Wooten, and Tannir (2005). Our goal is to improve the median RFS from 8 months (based on historical treatment) to 10.5 months using lenalidomide maintenance therapy. It is assumed that the RFS time is exponentially distributed with a median of  $\lambda_E$  among patients who receive lenalidomide as a maintenance therapy, and a median of  $\lambda_H$  is assumed for the historical treatment. Further, we assume that  $\lambda_H$  follows an inverse gamma distribution, i.e.,  $\lambda_H \sim \text{IG}(3.6, 20.8)$ , which has a mean of 8 months and variance of 40. To reflect the little prior knowledge of  $\lambda_E$  we assume an inverse gamma prior distribution with the same mean of 8 months and a much larger variance of 500, i.e.,  $\lambda_E \sim \text{IG}(2.128, 9.024)$ . The trial will be stopped early if  $\text{Pr}(\lambda_E > \lambda_H + \delta | \text{data}) < pL$ , where  $\delta = 2.5$  months and  $pL=0.05$  and this futility monitoring rule will be first applied when 10 patients have been enrolled. A maximum of 50 patients will be enrolled into this study at an expected accrual rate of 1 patient per month. From historical experience, 25% of patients in this cohort may become eligible for stem cell transplant and may come off study. For purposes of this analysis, these patients will be censored at the time of receiving transplant. Patients will be followed up for an additional 12 months after all patients have been enrolled. The trial will be conducted using the Clinical Trial Conduct (CTC) website maintained by the Department of Biostatistics at MDACC.

The operating characteristics of the design, based on an overall assumed accrual rate of 2 patients per month with 5000 simulated trials per scenario, are given in the following table. One-Arm Time-to-Event Simulator (version3.0.1) was used for the design and simulation.

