### **9.1.7 Relapse-free survival (RFS)**

Time from CR or CRi until confirmed relapse or death.

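### CR duration is counted from CR/CRi although patients start lenalidomide later, still in remission, so it includes relapse-free time that precedes the drug

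*Combined protocol and SAP*

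**What the plan says.** Section 9.1.9 starts the CRd clock at remission: "Time from CR or Cri until date of first objective documentation of confirmed relapse". CRd is a named secondary objective in section 1.2: "To assess the duration of remission (CRd) of patients with AML treated with lenalidomide maintenance". Section 4.0 goes further and lists CR duration, with RFS and OS, among the outcomes on which the effect of lenalidomide maintenance is to be determined.

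Entry comes later than CR. Section 3.1 uses the same window for first and second remission: "CR or CRi within 12 months of enrollment and are not immediately candidates for allogeneic stem cell transplant". It also states: "Patients should have received induction chemotherapy for AML and at least 1 consolidation". Section 8 describes the study population as "in patients with high risk AML and in first or second remission".

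The other time-to-event endpoints mostly start at treatment. In section 8, RFS is "defined as the time interval from date of treatment start until the date of death or disease relapse". Section 9.1.8 defines EFS as "Time from treatment start until date of first documented event", and section 9.1.10 also starts OS at treatment start. The exception is section 9.1.7, where RFS is "Time from CR or CRi until confirmed relapse or death". That is the CRd origin, and it contradicts section 8.

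Neither section 8 nor section 9 gives a delayed-entry adjustment, a landmark, or a summary of the interval from CR to first dose. Section 8 does not mention CRd at all.

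**The concern.** A patient who relapses between CR and first dose does not enter the trial. Every enrolled patient therefore brings a stretch of time, from CR to first dose, in which relapse could not have been observed. Counting CRd from CR adds that stretch to each patient's result. This is the usual immortal-time (left-truncation) problem.

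The CR date is a natural origin for describing how long a remission lasted. The difficulty comes from the use stated in section 4.0, where CRd is to show what lenalidomide does. Part of each interval was accrued before the first capsule. With no control arm, the result can only be set against figures from elsewhere, and a CRd lengthened by the entry lag could be taken as a sign of drug activity.

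**Working it through.** **Inputs from the documents.** Entry up to 12 months after CR/CRi, after induction and at least one consolidation (section 3.1); in remission at entry (section 8); exponential RFS with a historical median of 8 months and a goal of 10.5 months (section 8); expected RFS of 8.5 months (section 2.4). The plan gives no median, target or power for CRd, so there is no CRd figure to reproduce. The section 8 model from which the 8 months is borrowed is internally consistent. IG(3.6, 20.8) has mean 20.8/2.6 = 8 and variance 8²/1.6 = 40. IG(2.128, 9.024) has mean 9.024/1.128 = 8 and variance 8²/0.128 = 500.

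**Assumptions.** The RFS medians stand in for time to relapse, as illustration only. The hazard is constant, the drug is inactive and there is no censoring. The lag distribution is not in the documents, so several are shown.

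**Step 1, direction.** For each patient, CRd from CR = lag + time from treatment start to relapse. Any positive lag makes the first longer than the second, whatever the hazard.

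**Step 2, fixed lag L.** With a constant hazard, time from treatment start has the same median M as time from CR in unselected patients. The median CRd among enrolled patients is M + L.

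**Step 3, entry spread evenly over 0 to 12 months, enrolled only if still in remission.** The fraction still in remission at entry is q = (1 − 2^(−12/M)) / (12 × ln2/M). Beyond 12 months, the proportion of enrolled patients still relapse-free is 2^(−t/M)/q, so the median is M × log2(2/q). For M = 8: q = (1 − 0.3536)/1.0397 = 0.622, and the median is 8 × log2(3.217) = 8 × 1.686 = 13.5 months. The same formula gives 14.0 for M = 8.5 and 16.1 for M = 10.5. Simulation with 1,000,000 draws gives the same three values.

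**Results for M = 8 and an inactive drug (months):**

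| Lag from CR to treatment | Median from CR | Median from treatment start |
|---|---|---|
| Fixed 1 | 9.0 | 8.0 |
| Fixed 2 | 10.0 | 8.0 |
| Fixed 3 | 11.0 | 8.0 |
| Fixed 6 | 14.0 | 8.0 |
| Fixed 12 (limit of the window) | 20.0 | 8.0 |
| Spread over 0–12, still in remission | 13.5 | 8.0 |
| Spread over 1–12, still in remission | 14.1 | 8.0 |

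In the 0–12 case the mean lag of those enrolled is 5.0 months and the excess in the median is 13.5 − 8.0 = 5.5 months. If the lags of enrolled patients were themselves uniform, the median from CR would be 11.1 months for 0–6 and 14.5 for 0–12.

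**Step 4, would delayed entry repair it?** Keeping CR as origin and entering each patient into the risk set at treatment start gives 8.0 months for lags of 0–12. It gives 9.0 for 1–12 and about 11 for 3–12, and with a fixed 3-month lag it stays at 11.0. Nobody is at risk before the shortest lag, so that stretch cannot be estimated. The consolidation requirement makes some minimum lag likely. Precision is also poor. With 50 patients and lags of 0–12, 95% of simulated delayed-entry medians lie between about 0.4 and 13 to 14 months, against about 5 to 12 months counted from treatment start.

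**The case against.** The strongest reply is that a remission begins at CR, so time from CR to relapse is each enrolled patient's actual remission duration, and CR is a usual origin for it. That stands. A reader might infer that section 9.1.9 is simply a wrong definition, but the documents do not support that. What is missing is a rule that separates pre-treatment time from time on lenalidomide when CRd is used for the aim in section 4.0.

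Second, CRd is secondary, with no target, test or named comparator. That also stands. A reader might infer that CRd would look favourable against any historical figure, but a series from another maintenance trial with the same origin and a similar entry delay would carry a similar lag. The 8 and 8.5 months in sections 8 and 2.4 are RFS figures whose time origin is not stated, and the 10.5-month goal is for RFS.

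Third, the drug's effect is also assessed by endpoints that start at treatment. That limits the consequence but does not correct CRd.

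Fourth, the lag distribution is assumed, and with lags of a month or two the excess is only 1 to 2 months. That is correct. The excess would vanish only if every patient started treatment at CR, which is implausible given the required consolidation.

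**Conclusion.** The point holds as a matter of how CRd is estimated and read. As a measure of lenalidomide's effect, CRd from CR/CRi overstates on-treatment remission by about the entry lag. With a true median of 8 months and an inactive drug, the excess is 1 to 3 months for fixed lags of 1 to 3 months and about 5.5 months when entry is spread over the 12-month window. The direction follows from the definition and the entry rule. The size depends on the assumed lags and a constant hazard.

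Two stronger readings are not supported. One is that the primary result is inflated: section 8 counts RFS from treatment start, so its analysis, the futility and toxicity rules and the maximum of 50 patients stand. RFS would carry the same excess only if section 9.1.7 were applied, which is why that conflict needs settling. The other is that the plan will overstate relapse through a one-minus-survival curve that ignores deaths. Section 9.1.9 names no estimator or censoring rule, so for deaths without relapse there is missing detail, not a stated error.

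**What to change.** 1. To assess lenalidomide, define duration of remission from treatment start to confirmed relapse, in line with section 8 RFS, EFS and OS.
2. Keep CRd from CR/CRi as a descriptive figure only. Tabulate the CR-to-treatment interval beside it and state that it includes time before treatment.
3. If an estimate on the CR time scale is wanted, allow a delayed-entry analysis as a sensitivity analysis only. State that it does not correct for a minimum lag and will be imprecise with 50 patients.
4. Reconcile section 9.1.7 with section 8 in the same edit, so that RFS has one time origin.

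The cost is a change of wording in section 9 and an added line in section 8. The dates of CR/CRi and first dose are already needed for eligibility and for the existing endpoints, so no new visits, data or patients are required. The downside is that the reported duration will be shorter than one counted from CR and less directly comparable with series that count from CR. The descriptive figure in item 2 keeps that comparison available, with its limits shown.

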### **9.1.10 Overall survival (OS)**

Time from date of treatment start until date of death due to any cause.

## **10. REGULATORY AND REPORTING REQUIREMENTS**

### **10.1 Regulatory and Reporting Requirements**

**CTCAE term (AE description) and grade:** The descriptions and grading scales found in the CTEP Active Version of the NCI Common Terminology Criteria for Adverse Events (CTCAE) will be utilized for AE reporting. The CTEP Active Version of the CTCAE is identified and located on the CTEP website at:

[http://ctep.cancer.gov/protocolDevelopment/electronic\\_applications/ctc.htm](http://ctep.cancer.gov/protocolDevelopment/electronic_applications/ctc.htm). All appropriate treatment areas should have access to a copy of the CTEP Active Version of CTCAE.

Refer to Section 10.2 for Leukemia-Specific Adverse Event Recording Guidelines. The Principal Investigator will sign the PDMS Case Report Form toxicity pages per each patient at the completion of each course. Following signature, the Case Report Form will be used as source documentation for the adverse events.

## 10.2 Leukemia-specific Adverse Event Recording and Reporting Guidelines

These guidelines serve to bring the Department of Leukemia in compliance with the institutional policy on Reporting of Serious Adverse Events-definition of expected AE-“ All clinical protocols should include a list of the expected and anticipated events or hospitalizations relating to the study treatment” and Guideline for Good Clinical Practice 4.11.1 “All serious adverse events (SAEs) should be reported immediately to the sponsor except for those SAEs that the protocol or other document (e.g., Investigator’s Brochure) identifies as not needing immediate reporting”.

Adverse event is any untoward medical occurrence that may present during treatment with a pharmaceutical product but which does not necessarily have a causal relationship with this treatment.

Adverse drug reaction is a response to a drug which is noxious and unintended and which occurs at doses normally used in man for prophylaxis, diagnosis, or therapy of disease or for the modification of physiologic function.

Assessing causal connections between agents and disease is fundamental to the understanding of adverse drug reactions. In general, a drug may be considered a contributory cause of an adverse event if, had the drug not been administered, 1) the event would not have happened at all, 2) the event would have occurred later than it actually did, or 3) the event would have been less severe.

Adverse Events (AEs) will be evaluated according to current CTC version in each protocol. Only unexpected AEs will be recorded in the Case Report Form (CRF). Expected events during leukemia therapy are:

1. *Myelosuppression related events (due to disease or leukemia therapy)*
  - a. *febrile or infection episodes not requiring management in the intensive care unit*
  - b. *epistaxis or bleeding except for catastrophic CNS or pulmonary hemorrhage*
  - c. *anemia, neutropenia, lymphopenia, thrombocytopenia, leukopenia, leukocytosis*
2. *Disease related events*
  - a. *symptoms associated with anemia*
    - i. *fatigue*
    - ii. *weakness*
    - iii. *shortness of breath*
  - b. *electrolyte abnormalities (sodium, potassium, bicarbonate, CO2, magnesium)*
  - c. *chemistry abnormalities (LDH, phosphorus, calcium, BUN, protein, albumin, uric acid, alkaline phosphatase, glucose)*
  - d. *coagulation abnormalities*
  - e. *disease specific therapy (induction, maintenance, salvage, or stem cell therapy)*
  - f. *alopecia*
  - g. *bone, joint, or muscle pain*
  - h. *liver function test abnormalities associated with infection or disease progression*
    - i. *disease progression*
3. *General therapy related events*
  - a. *catheter related events*

- b. renal failure related to tumor lysis syndrome or antibiotic/antifungal therapy*
- c. rash related to antibiotic use*

#### **4. Hospitalization for the management of any of the above expected events**

Abnormal hematologic values will not be recorded on the CRF. For abnormal chemical values grade 3 or 4, the apogee will be reported per course in the CRF.

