## 2.2 Lenalidomide in AML

Lenalidomide, a derivative of thalidomide is currently approved for the treatment of multiple myeloma (MM) and MDS (myelodysplastic syndrome), but has been shown to have single-agent activity in AML as an induction – maintenance strategy. In a phase II trial of older patients (age  $\geq 60$  yrs) with untreated AML, lenalidomide was given at a high ‘induction’ dose, of 50 mg orally daily on a 28 day cycle (for up to 2 induction cycles), followed by a lower ‘maintenance’ dose of 10 mg orally daily for up to 12 months. The CR/CRI rate was 30% overall and 53% in patients who completed all of the high-dose therapy. The median CR duration was 10 months (1 – 17+ months). The treatment was well tolerated in this cohort of patients, with the most common grade 3-4 toxicities being myelosuppression and infection. Based on this data of single agent activity in AML and its longer-term use in AML, MDS, and MM we propose to use this as a maintenance strategy for higher-risk patients who are in remission after induction/consolidation therapy. The exact mechanism of action of lenalidomide is not known, but may involve immunomodulatory activity and reversal of an immunosuppressive environment present in

malignancy.

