**6.2 Myelosuppression:** Patients with leukemias and MDS usually present with abnormal peripheral blood counts at the time therapy is started and some myelosuppression is an expected event during the course of therapy for acute leukemias and myelodysplastic syndromes. Thus, dose-adjustments or treatment interruptions for myelosuppression will be planned only for confirmed, severe neutropenia or

thrombocytopenia that is confirmed for at least 1 week according to the following guidelines:

6.2.1.1 Patients in remission who have sustained low counts (for at least 7 days) of neutrophils  $<0.5 \times 10^9/L$  or a platelet count  $<20 \times 10^9/L$  should have therapy held until resolution. The patient may then receive subsequent treatment at 1 dose level reduction. A reduction of 2 dose levels may be considered if the myelosuppression was deemed severe and/or life threatening by the treating physician, and if it is in the patient's best interest.

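### The plan keeps all low blood counts off the CRF and plans no other capture or summary, leaving the safety objective without planned data on non-serious grade 3-4 neutropenia and thrombocytopenia

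*Combined protocol and SAP*

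**What the plan says.** Section 10.2 (Leukemia-specific Adverse Event Recording and Reporting Guidelines) closes two routes by which a low count could reach the CRF.

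- **Laboratory values.** "Abnormal hematologic values will not be recorded on the CRF". There is no grade limit. The next sentence treats chemistry differently: "For abnormal chemical values grade 3 or 4, the apogee will be reported per course in the CRF".
- **Adverse event terms.** "Only unexpected AEs will be recorded in the Case Report Form (CRF"). The list of expected events opens with "Myelosuppression related events (due to disease or leukemia therapy") and includes "anemia, neutropenia, lymphopenia, thrombocytopenia, leukopenia, leukocytosis". Cytopenia caused by therapy is therefore covered by the exclusion.

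Section 10.1 says that the signed CRF serves as source documentation for adverse events.

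Other sections give these counts a role in the trial. Section 1.2 lists as a secondary objective "To assess toxicity and safety of lenalidomide maintenance in patients with AML", with no restriction to non-hematologic events. Section 2.2 describes the cited lenalidomide trial in AML as well tolerated, "with the most common grade 3-4 toxicities being myelosuppression and infection". Section 6.2.1.1 has therapy held for neutrophils below 0.5 or platelets below 20 x 10^9/L sustained for at least 7 days, and continues: "The patient may then receive subsequent treatment at 1 dose level reduction".

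**The concern.** The recording rule and the safety objective do not fit together. The protocol acts on low counts by interrupting treatment and allowing a lower dose level, but it does not collect them as safety data. A report drawn from the CRF could call maintenance tolerable without any rate of severe neutropenia or thrombocytopenia. In a single-arm trial, tolerability can be judged only from what is recorded.

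Two planned analyses are touched as well. Event-free survival (section 9.1.8) counts withdrawal for an adverse event, so a withdrawal for non-serious cytopenia would be an endpoint event with no matching adverse event on the CRF. Section 8 plots immune parameters against the maximum toxicity grade experienced. If that grade is taken from CRF adverse events, it omits non-serious hematologic grades.

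**Working it through.** **1. Does anything else in the plan capture or summarize hematologic toxicity?**

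- Section 5.2b requires a CBC at least weekly in cycle 1, every 2 to 4 weeks in cycles 2 to 6, then every 4 weeks. The counts exist, but nothing says that they enter the trial dataset.
- Serious adverse event reporting (section 10) applies to any event meeting a seriousness criterion, and names blood dyscrasias among the examples of important medical events. Serious cytopenias can be reported this way. An ordinary grade 3-4 cytopenia need not be.
- Section 8 monitors toxicity, but defines it as treatment-related, clinically significant grade 3 or 4 non-hematologic events. It has no table or estimate for hematologic toxicity.

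None of the three is a planned capture or summary of non-serious grade 3-4 cytopenia.

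**2. Is the toxicity stopping rule itself in error?** Inputs from section 8: a Beta(0.6, 1.4) prior, and stop if Pr(rate > 0.30 | data) > 0.92, with boundaries stated at 10, 20, 30, 40 and 50 patients. With x toxicities in n patients the posterior is Beta(0.6 + x, 1.4 + n - x). The boundary is the smallest x at which the posterior probability exceeds 0.92.

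| n | probability one below boundary | boundary x | probability at boundary |
|---|---|---|---|
| 10 | 0.8798 | 6 | 0.9625 |
| 20 | 0.9059 | 10 | 0.9608 |
| 30 | 0.8630 | 13 | 0.9286 |
| 40 | 0.9003 | 17 | 0.9459 |
| 50 | 0.8761 | 20 | 0.9262 |

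These equal the stated boundaries 6/10/13/17/20. Exact sequential binomial calculation, counting stops at 10, 20, 30 and 40 as early, gives stopping probabilities of 0.0002, 0.0101, 0.1353, 0.5419 and 0.9043 at true rates of 0.10 to 0.50. The protocol states 0.0002, 0.010, 0.135, 0.542 and 0.904. The rule is sound for what it counts, and it counts no hematologic events.

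**3. What could be estimated if the counts were recorded?** The documents give no rate of grade 3-4 neutropenia or thrombocytopenia for patients in remission on maintenance dosing, so a range of rates is assumed. With the maximum N of 50 (section 8), the approximate 95% half-width is 1.96 x sqrt(p(1 - p)/50):

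- p = 0.10: 1.96 x sqrt(0.09/50) = 0.083
- p = 0.30: 1.96 x sqrt(0.21/50) = 0.127
- p = 0.50: 1.96 x sqrt(0.25/50) = 0.139

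These figures show the precision available to the trial. They do not measure harm from the gap.

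**The case against.** The strongest reply is that little is really lost. This is a single-institution study, CBCs are drawn throughout, and nothing forbids extracting them later. Serious cytopenias have the SAE route. The exclusion is a departmental convention tied to institutional policy, and no primary analysis or stopping boundary depends on it. All of this is correct. It limits the point to planned capture and reporting, but does not supply the missing plan.

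A reader might infer more than the text supports:

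- **That hematologic toxicity cannot be reported, or would be recorded as zero.** This goes too far, because records and SAE reports would hold some of it. The statement holds only for non-serious events on the CRF.
- **That dose reductions could not be traced.** Section 10.2 does not bar dose data, and section 8 reports correlative data by dose level. What may be missing is the hematologic reason for a change.
- **That myelosuppression is known to be the leading toxicity here.** Section 2.2 names it jointly with infection, in older patients with untreated AML who began with a 50 mg induction phase.
- **That a new severe cytopenia in remission is probably due to the drug.** Section 3.1 admits patients with neutrophils just above 0.5 and platelets of 30 x 10^9/L, close to the hold thresholds. CRi qualifies, dysplasia and persistent residual disease are qualifying risk features, and section 4.0 lets some relapsing patients stay on study. Disease or prior chemotherapy is a credible cause.

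The last item affects how a rate would be interpreted. It is a reason to record baseline counts and relapse status, not a reason to leave the events out.

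**Conclusion.** The concern stands as a gap in planned capture and reporting. Section 10.2 excludes abnormal counts and cytopenia events from the adverse event source document without regard to grade, and no other section replaces them. A stated secondary objective is therefore left without planned data on non-serious grade 3-4 neutropenia and thrombocytopenia, although low counts govern treatment holds. The primary endpoint and the non-hematologic stopping rule are unaffected.

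The true rate is unknown, so no size can be put on what would be missed. The half-widths of about 8, 13 and 14 percentage points rest on assumed rates of 10%, 30% and 50% and on full enrollment of 50. The 30% is not taken from any hematologic figure; the protocol's own 30% is its non-hematologic monitoring threshold. This is a change the trial should make, but the trial does not fail without it.

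**What to change.** In section 10.2, replace the exclusion of hematologic values with a requirement to record on the CRF:

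- the worst grade 3-4 neutrophil and platelet value per course, as is already done for chemistry;
- the baseline neutrophil and platelet counts;
- each episode meeting section 6.2.1.1;
- the reason for any resulting hold or dose-level change.

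In section 8, add the proportion of patients with grade 3-4 neutropenia, with grade 3-4 thrombocytopenia, with a section 6.2.1.1 episode, and with a resulting hold or dose-level change, each with a 95% interval. Present these alongside baseline counts and relapse status, because attribution to the drug is uncertain. State that the worst value is the worst observed on the section 5.2b schedule, which becomes sparser after cycle 1.

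Leave the non-hematologic stopping rule and the clinical rules unchanged.

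This is a cheap improvement, since the counts are already drawn and the per-course mechanism exists. The cost is some extra data entry and a departure, for this protocol, from the departmental recording convention.
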